Continuous Glucose Monitoring in Patients with End-Stage Kidney Disease and Burnt-Out Diabetes

1. Study Summary

| | |
|---|---|
| Project Title | Continuous Glucose Monitoring in Patients with End-Stage Kidney Disease and Burnt-Out Diabetes |
| Project Design | Observational cross-sectional study. |
| Primary Objective | 
To determine if utilizing Continuous Glucose Monitor (CGM) devices is superior to HbA1c for assessing glycemic control in patients with end-stage kidney disease on dialysis. |
| Secondary Objective(s) | 
Compare daily mean glucose values between patients with burnt-out diabetes and non-diabetic subjects with ESKD. |
| Research Intervention(s)/Interactions | 
Continuous glucose monitoring (CGM) compared to glycemic metrics including CGM and HbA1c. |
| Study Population | Individual with and without diabetes on hemodialysis and with HbA1c < 6.5% on no diabetes therapy will be eligible to enroll. |
| Sample Size | 40 patients. 20 patients with burnt-out diabetes and 20 non-diabetic subjects with ESKD |
| Study Duration for individual participants | 10 days |
| Study Specific Abbreviations/ Definitions | POC, Bedside point-of-care; CGM, Continuous glucose monitoring; T2D, Type 2 diabetes; BG, blood glucose; OAD, Oral antidiabetic; MARD, mean absolute relative difference; CBG, capillary blood glucose |
| Funding Source (if any) | N/A |

2. Objectives

Diabetes is the number one cause of end stage kidney disease (ESKD) and need for dialysis. It is estimated that diabetes affects up to 40% of patients with ESKD³. Glycosylated hemoglobin (HbA1c) is the gold standard to assess glycemic control in patients with diabetes and indicates the average glycemia during the past 2-3 months. In subjects with ESKD; however, the accuracy of HbA1c is reduced because of anemia, shortened erythrocyte lifespan, erythropoietin therapy, among others factors. To overcome the limitations of HbA1c, continuous glucose monitoring (CGM) technology has been shown to provide a comprehensive glycemic control in patients with diabetes and may overcome the limitations of these methods in the ESKD population; however, the accuracy of CGM in ESKD has not been established.

About one fourth of patients with diabetes on dialysis therapy experience resolution of their hyperglycemia, as defined by an HbA1c less than 6.5%, without antidiabetic therapy. This

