Continuous Glucose Monitoring in Patients with End-Stage Kidney Disease and Burnt-Out Diabetes

phenomenon is known as “burnt-out diabetes”. Because HbA1c may be falsely low in ESKD, we will use CGM to assess glycemic control and confirm whether patients with burnt-out diabetes have normoglycemia or not. We hypothesize that the use of CGM may represent a better tool to assess glycemic control than HbA1c in patients with ESKD on dialysis. To prove this hypothesis, we will compare glycemic metrics including CGM and HbA1c, in 20 patients with burnt-out diabetes and in 20 non-diabetic subjects with ESKD.

II. Specific Aims:

Study Aim. Compare glycemic metrics including CGM and HbA1c in patients with burnt-out diabetes and in non-diabetic subjects with ESKD.

Hypotheses:

1. The use of CGM represents a better tool to assess glycemic control than traditional markers (HbA1c) in patients with ESKD and renal replacement therapy (dialysis). Patients with burnt-out diabetes will show higher mean daily glucose values and higher time-above range (TAR > 180 mg/dl) compared to non-diabetic subjects with ESKD.

3. Background

Diabetes and chronic kidney disease. More than 37 million adults, or 14.7% of all Americans aged 18 and older, are living with diabetes. Controlling hyperglycemia is foundational to diabetes management and is necessary to reduce the risks of chronic diabetes complications and death. Diabetic nephropathy accounts for great morbidity, as diabetes is the number one cause of chronic kidney disease (CKD) and end stage kidney disease (ESKD) in the US². It is estimated that diabetes affects up to 40% of patients with ESKD³.

Assessment of glucose control in patients with advanced CKD/ESKD is complex due to changes in glucose homeostasis, potential effects on assays of glycemia, and altered pharmacokinetics of diabetes medications². Glycosylated hemoglobin (HbA1c) has been the gold standard to assess glycemic control in patients with diabetes. HbA1c reflects the average glycemic value over approximately 3 months. Although HbA1c is associated with chronic complications of diabetes in patients with normal kidney function, its predictive value is uncertain in patients with increased red cell turnover (hemolysis) and in subjects with ESKD or eGFR <30 ml/min. HbA1c reliability in ESKD is reduced because of anemia, shortened erythrocyte lifespan, protein-energy wasting, and malnutrition-inflammation cachexia syndrome, among others^{4,5}.

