To overcome the limitations of HbA1c, alternative methods to assess long-term glycemic control have been proposed including fructosamine and glycated albumin². Fructosamine measures ketoamines formed by non-enzymatic glycation of serum proteins. It is a useful index for glycemic control over the prior 2 to 4 weeks, and some studies have reported that fructosamine more accurately reflects blood glucose control than HbA1c in anemic patients with ESKD on dialysis. However, there may be falsely low readings in the presence of hypoalbuminemia due to protein-energy wasting and in peritoneal dialysis due to dialysate

Continuous Glucose Monitoring in Patients with End-Stage Kidney Disease and Burnt-Out Diabetes

protein loss. Glycated albumin is a useful marker reflecting glycemic control over the prior 2 to 4 weeks. In patients with ESKD, glycated albumin more rapidly reflects the status of blood glucose control than HbA1c. Like fructosamine, there is potential for falsely low readings in patients with peritoneal dialysis with dialysate protein losses and hypoalbuminemia^{2,5-8}.

Continuous glucose monitoring (CGM) technology in the outpatient setting has transformed glucose monitoring for diabetes self-management, providing more comprehensive glycemic control data than intermittent point-of-care capillary blood glucose monitoring and HbA1c. Although the accuracy of CGM in ESKD has not been established, a recent prospective study in hospitalized patients with type 1 and type 2 diabetes reported good accuracy of CGM in patients with CKD⁹.

Burnt-out diabetes. Once progressed to ESKD, up to one fourth of patients experience resolution of their hyperglycemia, as defined by an HbA1c level of less than 6.5%, and consequently are no longer on antidiabetic agents and insulin. This phenomenon is known as “burnt-out diabetes” which is likely due to various underlying factors, including but not limited to, malnutrition, reduced clearance and degradation of insulin, decreased kidney gluconeogenesis, and accumulation of uremic toxins¹⁰. These patients are likely at a greater risk of morbidity and mortality and an increased risk of hypoglycemic episodes⁴. There is a need for further research in patients with ESKD to establish what is the most appropriate tool to assess glycemic control in those with ‘burnt-out diabetes’.

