Our study will use CGM to measure patients’ glucose with real-time levels as opposed to relying on surrogate markers like A1c. These results can give insight into the reality of glycemic control in these patients and can impact the best monitoring and treatment for patients with burnt-out diabetes. It is not known if patients with burnt-out diabetes have complete normoglycemia or if they may have episodes of (untreated) hyperglycemia, which may be associated with poor outcome. Accordingly, we will compare glycemic control by CGM in patients with burnt-out diabetes and non-diabetic patients with ESKD.

4. Study Endpoints

Primary safety and efficacy endpoints:

- 1) Frequency of overall and nocturnal hypoglycemia (< 70 mg/dl) by Dexcom G6 CGM (safety endpoint) ⁵².
- 2) Glycemic control, as measured by mean daily glucose concentration between groups by Dexcom G6 CGM (efficacy endpoint).

5. Study Intervention/Investigational Agent

The proposed CGM to be used in this study is the Dexcom G6, a factory-calibrated CGM system, that is innovative in many aspects: 1) it does not require finger stick glucose testing for calibration, 2) the sensor is small, compact, light-weight, 3) has no interference with several substances and drugs, and 4) effective glucose measures every 5 minutes (288 glucose measures per day).

6. Procedures Involved

Visit 1: All consenting subjects, with and without diabetes, will have a blinded Dexcom G6 CGM placed for up to 10 days (study duration). Consent procedure will be conducted during/after their hemodialysis sessions after explaining all study procedures. After providing informed consent, patients will have a sensor inserted by the study team. Insertion of the CGM sensor will be performed per manufacturer instructions and following an aseptic technique. After insertion of the sensors, providers will ensure proper hemostasis is achieved. Sensors will be removed if prolonged bleeding or severe pain occurs. Patients will be educated on study procedures and sensor care. The participants will be instructed to wear the CGM with the display off for 10 days while continuing regular, routine dialysis sessions. They will be instructed that the device will be removed at a future dialysis session after 10 days of wear.

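### The primary objective is to show that CGM is superior to HbA1c, but the plan has no CGM–HbA1c analysis, superiority criterion or reference glucose that could show it, and its primary endpoint differs between sections

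*Combined protocol and SAP*

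**What the plan says.** Section 1 gives the primary objective as "To determine if utilizing Continuous Glucose Monitor (CGM) devices is superior to HbA1c for assessing glycemic control". The first sentence of hypothesis 1 in Section 2 likewise calls CGM the better tool, and the text before it says how this will be settled: "To prove this hypothesis, we will compare glycemic metrics including CGM and HbA1c", in two groups of 20.

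The methods are these:
- **Section 4** lists "Glycemic control, as measured by mean daily glucose concentration between groups by Dexcom G6 CGM" as the efficacy endpoint.
- **Section 20** names two-sample t or Wilcoxon tests for clinical characteristics and a linear regression for the group difference. Continuous secondary outcomes, with the most recent HbA1c on the list, are to be handled like the primary.
- **Section 7** lists CGM outcomes, including percentage of time above 180 and above 250 mg/dL, with no analysis linking them to HbA1c.

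On a reference standard, Section 2 states that "the accuracy of CGM in ESKD has not been established". Section 3 repeats this and cites good accuracy in hospitalized patients with CKD. Point-of-care testing appears in the outcome definitions of Section 6, but neither visit includes it. HbA1c comes from the medical record (Section 6) and must be below 6.5% at entry (Section 11).

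The primary endpoint varies by section:

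| Item | Primary in | Secondary in |
|---|---|---|
| Group difference in CGM mean glucose | Section 4 | Section 1 ("Compare daily mean glucose values between patients with burnt-out diabetes and non-diabetic subjects with ESKD"), Section 20 |
| Hypoglycemia ("Frequency of overall and nocturnal hypoglycemia") | Sections 4 and 6 | – |
| An unspecified set of glycemic metrics, CGM and HbA1c among them | Section 20 | – |
| CGM superior to HbA1c (objective) | Section 1 | – |

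**The concern.** A claim that one measurement method is better than another needs a standard to judge both against, or at least a rule for what counts as better. The plan has neither. If it is followed as written, a significant CGM contrast beside a non-significant HbA1c contrast could be reported as proof that CGM is the better tool, although CGM error can produce the same pattern. Two contrasts that agree could be reported as showing that HbA1c is sound, although HbA1c may read low in everyone on dialysis. Because the sections disagree about the primary, the result given that label could also be chosen after the data are seen.

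**Working it through.** **The plan's own figure.** The only design figure is 40 patients (20 + 20), described in Section 7 as a pilot. No effect size, SD, power or superiority margin is given, so there is no calculation to reproduce.

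**What the planned quantities identify.** Among enrolled patients in group g (1 = burnt-out, 0 = non-diabetic), let m_g be true mean glucose, c_g the mean CGM over-reading, and u_g the mean HbA1c under-reading on the glucose scale. Then:
- CGM contrast = (m₁ − m₀) + (c₁ − c₀)
- HbA1c contrast = (m₁ − m₀) − (u₁ − u₀)
- gap between the contrasts = (c₁ − c₀) + (u₁ − u₀)
- mean within-patient discordance (CGM minus HbA1c-implied glucose) in group g = c_g + u_g

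CGM error and HbA1c error enter only as a sum. Whether c is smaller than u, which superiority would require, cannot be recovered without a reference glucose.

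Take two opposite truths, in SD units and before the HbA1c cut-off is applied. If glucose differs by 1.0 and HbA1c reads 1.0 low in burnt-out patients, the CGM contrast is 1.0 + 0 = 1.0 and the HbA1c contrast is 1.0 − 1.0 = 0. If glucose is equal and CGM reads 1.0 high in burnt-out patients, they are 0 + 1.0 = 1.0 and 0 − 0 = 0. The expected contrasts are identical.

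**Simulation (illustration only).** From the documents: 20 + 20, and an HbA1c cut-off that acts on eligibility. Assumed, in units of the true-glucose SD: cut-off 1.0–1.5 above the non-diabetic mean, HbA1c noise 0.3–0.6, CGM error 0.1–0.5, two-sided t-tests at 0.05, 10,000 trials per scenario. The figures are the percentage of trials with the CGM contrast significant and the HbA1c contrast not.

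| Scenario | Error 0 | Error 0.5 | Error 1.0 |
|---|---|---|---|
| (a) HbA1c reads low in burnt-out only; true difference 1.0 | 7–26 | 54–72 | 82–93 |
| (b) CGM reads high in burnt-out only; HbA1c unbiased; no true difference; noise and CGM error 0.3 | – | 35–41 | 88–92 |
| (c) HbA1c reads low in both groups; true difference 1.0 | 7–27 | 5–23 | 5–20 |

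Row (a) shows that the contrasts carry some informal information about HbA1c error specific to the burnt-out group. Row (b) shows that the same pattern appears when CGM is the method in error. Row (c) shows that the pattern does not rise with HbA1c error common to both groups.

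**Common HbA1c error and selection.** In (c), under-reading admits patients with higher true glucose, because eligibility acts on HbA1c. With CGM error 0.3, as common under-reading goes from 0 to 1.0 SD:
- the HbA1c contrast moves from 0.47–0.62 to 0.71–0.86 SD;
- the CGM contrast moves from 0.52–0.70 to 0.77–0.88 SD;
- the share of burnt-out patients truly above the cut-off moves from 5–17% to 24–40%.

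Common error therefore shifts the contrasts without being identified by them. Absolute ranges such as time above 180 mg/dL would respond to it.

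**Would a within-patient analysis settle it?** Only in part. At equal glucose, mean discordance in burnt-out patients is 0.50–0.56 SD when HbA1c reads 0.5 low and 0.51–0.61 SD when CGM reads 0.5 high. It detects disagreement and cannot assign it.

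**What the answerable question would yield.** With 20 per group, the 95% CI half-width for a difference in means is about 2.024 × √(2/20) = 0.64 SD, unadjusted. Power reaches 80% at a difference of about 0.91 SD.

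**The case against.** The protocol has a working meaning for better tool. Hypothesis 1 goes on to predict higher mean glucose and more time above 180 mg/dL in burnt-out patients, and Sections 2 and 3 say CGM will show whether these patients are truly normoglycemic. Section 7's absolute ranges, in patients who all have HbA1c below 6.5%, address that without any group contrast. Section 1 also describes a comparison of CGM with metrics that include HbA1c. This is a small observational pilot. All of that stands, and it makes much of the problem one of over-claimed wording on an analysable question. It does not supply a test of superiority: no rule says how much time above 180 mg/dL contradicts a low HbA1c, no method is attached to the Section 1 comparison, and pilot status explains a missing power calculation but not a primary objective without an analysis.

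A reader might infer three stronger things that the documents do not support:
- **That the plan contains nothing but group contrasts.** Section 7's absolute ranges are listed outcomes.
- **That HbA1c error common to both groups cancels.** Because entry depends on HbA1c, it can shift both contrasts; it is unidentified, not absent.
- **That CGM is likely to over-read in burnt-out patients.** Both groups are dialysis patients wearing the same sensor, and nothing in the documents suggests a differential bias. Scenario (b) is a logical possibility, and its percentages are assumptions. The simulation also uses t-tests, not the adjusted regression of Section 20.

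**Conclusion.** The point holds. The plan can answer whether CGM glucose differs between the groups and whether CGM shows hyperglycemia despite HbA1c below 6.5%. It cannot establish that CGM is superior to HbA1c, and no sample size would change that without a reference glucose and a criterion. This conclusion rests on the text and the algebra; the simulated percentages only illustrate it. The conflict over the primary endpoint is a matter of record in Sections 1, 4, 6 and 20. Removing the superiority wording and naming one primary should be done before any analysis. The added descriptive analyses are worthwhile but less pressing.

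**What to change.** 1. **Objective.** In Sections 1 and 2, replace *superior* and *better tool* with one answerable primary objective. For example: to estimate the difference (95% CI) in CGM mean glucose between hemodialysis patients with burnt-out diabetes and those without diabetes, all with HbA1c below 6.5% and on no diabetes therapy. Align Sections 4, 6 and 20: name this as the outcome of the regression, remove it from the secondary lists, and label hypoglycemia as secondary or as an explicit co-primary.
2. **Secondary descriptive analyses.** Report time above 180 mg/dL in each group, and within-patient discordance (CGM mean minus the glucose implied by HbA1c, using one conversion named in advance) with its mean and 95% CI by group. Record the date of each HbA1c. State that selecting on HbA1c below 6.5% pushes discordance upward, that the conversion may not hold in ESKD, and that the time windows differ (10 days against about 3 months). Optionally, report how the fructosamine and glycated albumin already drawn relate to CGM mean glucose and to HbA1c.
3. **Conclusion.** Limit it to the group difference, hyperglycemia despite HbA1c below 6.5%, and CGM–HbA1c discordance. State that the study cannot show which method is in error.

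The cost is a more modest headline claim, wording changes in five sections and a little extra analysis, with no new patients, visits or required assays.

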Patients will be consented- after explanation of the procedure- for withdrawing about 5 ml of blood prior to dialysis to measure glycated albumin as well as fructosamine to assess glycemic control in dialysis patients with and without diabetes.

Visit 2: The CGM sensor will be removed after 10 days, and data will be downloaded at this time. HbA1c will be collected from patient medical record. In addition, we will collect information on clinical characteristics (age, sex, duration of diabetes and ESKD, dialysis, history diabetes treatment, duration of burn-out period, time off diabetes medications, comorbidities (hypertension, coronary heart disease, heart failure, COPD).

Clinical trial materials will be labeled and should be handled and stored according to the respective hospital's regulatory requirements.

For the safety outcome (primary outcome), a "hypoglycemia episode" is defined as a glucose < 70 mg/dl, "clinically significant hypoglycemia" is defined as a glucose <54 mg/dl, and "severe hypoglycemia" is defined as a glucose < 40 mg/dl by POC testing or by CGM for > 15 minutes. An episode is not counted as being "new event" unless the sensor glucose is above 70 mg/dL or above 54 mg/dL at least once following an episode of hypoglycemia. A "hypoglycemic event rate" is defined as the number of hypoglycemic events per patient per day.

For the efficacy outcome, the "mean daily glucose concentration" is defined as the mean daily and fasting glucose concentration during the hospital stay up to first 10 days of therapy by POC testing and by CGM. A "nocturnal" hypoglycemia episode or a "nocturnal" clinically significant hypoglycemia episode is defined as an episode occurring during the time interval of 00:01 to 05:59.

7. Statistical Analysis Plan

Data Analysis. Data will be entered into REDCap to keep track of all results and to meet HIPAA and confidentiality regulations, provided by the Emory Research Information Technology Department. A p-value less than 0.05 will be considered significant. The data will be presented

Continuous Glucose Monitoring in Patients with End-Stage Kidney Disease and Burnt-Out Diabetes

as means \pm SD. Statistical analysis will be performed using the SAS (version 9.2; SAS Institute, Cary, NC). All statistical analysis will be performed by [name], from Emory University.

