To assure each subject's confidentiality, data collected under this protocol will be coded and stored in a secure locked file cabinet with access limited to those directly related to the conduct of this study. Electronic versions of these data will be stored on a limited access, password protected, secure server with coded patient identifiers. Study participants will be assigned a code number that will be linked to their name. Only study personnel will have access to the linked name-code key. Except for the informed consent form, data will be marked solely with the participant's code number.

Statistical analysis

The primary endpoint in this study is to compare glycemic metrics including CGM and HbA1c in patients with burnt-out diabetes and in non-diabetic subjects with ESKD. We will first compare clinical characteristics including demographics, duration of diabetes and dialysis between patients with and without DR using two-sample t-tests or nonparametric Wilcoxon tests. We will perform multivariate linear regression to evaluate the group difference while accounting other possible confounders (patient age, type of dialysis) for the primary outcome. The secondary endpoints include compare daily mean glucose values between patients with burnt-out diabetes and non-diabetic subjects with ESKD, most recent HbA1c, comorbidities (hypertension, cardiovascular disease, heart failure, peripheral neuropathy, autonomic/GI neuropathy, cerebrovascular disease, peripheral vascular disease, depression, anxiety, cognitive impairment/dementia), adherence and barriers to screening recommendations, we will analyze continuous secondary outcomes in the same way that we propose for the primary endpoint. A p-value less than 0.05 will be considered significant. The data will be presented as means \pm SD. Statistical analysis will be performed using the SAS (version 9.2; SAS Institute, Cary, NC).

Confidentiality

All data and records generated during this study will be kept confidential in accordance with Institutional policies and HIPAA on subject privacy. The Principal investigator and other study personnel will not use data or PHI for any purpose other than conduction of the study. All PHI used will be de-identified and coded by the Principal investigator or designee. The code will be kept in a password protected computer file. PHI will be disclosed when required for audit by regulatory agency.

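### Fructosamine and glycated albumin are measured without serum albumin, so a distortion that the protocol itself names, chiefly for fructosamine, can be neither seen nor examined

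*Combined protocol and SAP*

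**What the plan says.** - **The assays.** Section 6 (Procedures Involved) plans a pre-dialysis blood draw in both groups to "measure glycated albumin as well as fructosamine to assess glycemic control in dialysis patients with and without diabetes".
- **The warning on fructosamine.** Section 3 (Background) says that "there may be falsely low readings in the presence of hypoalbuminemia due to protein-energy wasting".
- **The warning on glycated albumin.** Section 3 continues: "Like fructosamine, there is potential for falsely low readings in patients with peritoneal dialysis with dialysate protein losses and hypoalbuminemia".
- **The possible link to the groups.** Section 3 describes burnt-out diabetes as "likely due to various underlying factors, including but not limited to, malnutrition". Earlier in the same section, protein-energy wasting and the malnutrition-inflammation syndrome are listed among the reasons why HbA1c is unreliable in ESKD, with no distinction by diabetes status.
- **The comparison.** The study aim in Section 2 is to "Compare glycemic metrics including CGM and HbA1c in patients with burnt-out diabetes and in non-diabetic subjects with ESKD".
- **What else is recorded.** At Visit 2, "we will collect information on clinical characteristics (age, sex, duration of diabetes and ESKD, dialysis, history diabetes treatment, duration of burn-out period"; the list goes on to time off diabetes drugs and comorbidities. It contains no serum albumin, total protein or nutritional measure.
- **Adjustment.** Section 20 (Statistical analysis) plans a regression "accounting other possible confounders (patient age, type of dialysis) for the primary outcome", with continuous secondary outcomes handled the same way. Albumin is not among the covariates it names.

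**The concern.** Section 3 introduces the two markers as ways round the weaknesses of HbA1c, and then says that they have a weakness of their own, tied to low albumin. The quantity needed to judge that weakness is not recorded. A low fructosamine value could then reflect low glucose or low albumin, and the dataset could not separate the two.

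Two uses of the markers would be exposed:

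1. **Comparison between groups.** If mean albumin differs between the groups, fructosamine differs for a reason unrelated to glucose. Lower albumin in the burnt-out group would work against the hypothesis in Section 2 that this group has higher glycemia. Lower albumin in controls would exaggerate that difference.
2. **Agreement with CGM.** Differences in albumin from patient to patient add scatter to fructosamine that CGM does not share, even when the group means are equal. Fructosamine could look like a poor match for CGM for a non-glycemic reason. In patients with low albumin it could also seem to support a low HbA1c.

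**Working it through.** The plan states no figure on this point, so there is nothing to reproduce. The check has a textual part and an illustrative part.

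**1. Is albumin recorded or used anywhere?** In the whole document, albumin appears only within the marker name glycated albumin and within the word hypoalbuminemia. It is absent from:
- the Section 6 data list;
- the outcome list in Section 7;
- the comorbidity list and named covariates in Section 20.

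The omission is confirmed.

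**2. How firm is the warning for each marker?**
- Fructosamine: the warning names hypoalbuminemia from protein-energy wasting separately from peritoneal dialysis losses, so it reaches hemodialysis patients. It is hedged as a possibility.
- Glycated albumin: the warning is worded around peritoneal dialysis. Section 1 describes a hemodialysis population, and the recruitment counts in Sections 7 and 12 are of hemodialysis patients. The inclusion criterion in Section 11 asks only for dialysis, however, and Section 20 adjusts for type of dialysis. This part is weaker but not clearly irrelevant.

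**3. Do the documents say that albumin differs between the groups?** No. Malnutrition is one likely factor in an open list of reasons why diabetes burns out, and wasting is linked to ESKD generally. An imbalance is possible and not established.

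**4. Size on the marker's own scale (all inputs assumed).** Take fructosamine as proportional to albumin at fixed glucose, control mean albumin 4.0 g/dL, and a fructosamine of 300 umol/L at that albumin.

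Ratio = albumin / 4.0

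| Mean albumin in the other group (g/dL) | Ratio | Fructosamine (umol/L) | Change |
|---|---|---|---|
| 4.0 | 4.0/4.0 = 1.00 | 300 | 0% |
| 3.8 | 3.8/4.0 = 0.95 | 285 | -5% |
| 3.0 | 3.0/4.0 = 0.75 | 225 | -25% |

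The same arithmetic applies to individuals: two patients in one group with equal glucose and albumin of 4.0 and 3.0 g/dL would read 300 and 225. That is the scatter at issue for agreement with CGM. The effect on glycated albumin depends on how it is expressed, which the plan does not state, and may be smaller.

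**5. What a shift would do to a group comparison (shifts assumed).** Inputs from the plan are 20 per group (Section 1) and a significance level of 0.05 (Sections 7 and 20). Sidedness is not stated, so two-sided is assumed. Normal approximation, SD = 1:

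- Standard error = sqrt(2/20) = 0.316.
- True difference detectable with 80% power = (1.960 + 0.842) x 0.316 = 0.89 SD.
- With the burnt-out group's marker pulled down by b SD, power for that difference = Phi((0.886 - b)/0.316 - 1.960).
- With no true difference, chance of a significant result = Phi(b/0.316 - 1.960) + Phi(-b/0.316 - 1.960).

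| Assumed shift b (SD) | Power to show a true 0.89 SD difference | Chance of a significant result with no true difference |
|---|---|---|
| 0 | 80% | 5% |
| 0.25 | 52% | 12% |
| 0.50 | 23% | 35% |
| 0.75 | 6% | 66% |

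The second table shows how sensitive a comparison of 20 with 20 would be. It is no evidence that any such shift is present in this study.

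**The case against.** **The bias is not shown to be differential.** A reader might infer from the mention of malnutrition that the protocol itself expects falsely low markers mainly in the burnt-out group. The text does not go that far. It gives malnutrition as one likely reason why hyperglycemia resolves, makes no comparison with non-diabetic dialysis patients, and links wasting to ESKD as a whole. This objection stands in full. With equal albumin in the two groups the mean bias is zero, although the scatter against CGM remains.

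**Both markers are not equally affected.** A reader might also take Section 3 to say flatly that both read low in hypoalbuminemia. The glycated albumin sentence carries a peritoneal dialysis qualifier, and both sentences are hedged. This stands too: fructosamine is the firm part.

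**No analysis of either marker is specified.** Neither is named in the objectives, the endpoints (Section 4), the outcome list in Section 7 or the analysis in Section 20. The comparison is a reading of the Section 2 aim and of the stated purpose of the draw. That limits the point to any use made of the markers. It does not remove it, because blood is taken for them and their stated purpose is to assess glycemic control.

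**The impact is limited.** Both primary endpoints come from CGM, the study is a 40-subject pilot, and albumin might be recoverable from records later. The first two points keep this to a modest recommendation. The third is a reason to write the item into the plan now, since retrieval near the draw date is then assured.

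**Adjustment can do harm.** If malnutrition also lowers glucose in truth, as Section 3 suggests for burnt-out diabetes, albumin partly marks a real glycemic difference and adjusting for it may remove some of that difference. Correcting fructosamine for albumin and then entering albumin as a covariate would also adjust twice. Both objections stand and shape the fix.

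**Conclusion.** The concern holds in a limited form. The plan measures two markers to assess glycemic control, states that low albumin may lower one of them (and, in the peritoneal dialysis setting, the other), and records nothing that would show whether this has happened. The fructosamine comparison is open to bias if albumin differs between the groups, and agreement between fructosamine and CGM is open to distortion even if it does not.

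The size is unknown. The documents support neither a known imbalance nor a known direction. The range of 0% to 25% rests on assumed proportionality and assumed albumin values, and the power figures rest on assumed shifts. The primary CGM results are untouched. This is worth correcting because it is cheap; the study's main conclusions do not depend on it.

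**What to change.** - **Section 6:** add serum albumin to the data list, abstracted from the dialysis record at the date nearest the blood draw. State the units in which glycated albumin is reported.
- **Section 20:** report serum albumin by group. For any group comparison or marker-CGM comparison using fructosamine or glycated albumin, show the unadjusted result together with one albumin-adjusted sensitivity analysis. For fructosamine, name in advance either an albumin-corrected value or albumin as a covariate, and do not use both. The documents give no correction formula, so one must be specified if that route is chosen.
- Leave the CGM analyses as they are.

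**Cost:** one abstracted value per subject (40 in all), a short addition to Section 20, and one extra sensitivity analysis. The adjusted result may remove some true glycemic difference, because malnutrition may also lower glucose. The unadjusted result should therefore stay beside it, and any gap between the two should be reported without treating the adjusted figure as the correct one.
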